After data has been collected and locked as an analysis dataset, missingness will be assessed for degree as well as randomness. If the amount of missing data is small, incomplete observations will be removed from analyses of interest. On the other hand, imputation using chained equations (MICE) or random forests may be applied in the case of observations that are missing at random.

Multiplicity

There will be only a single analysis of the primary outcome across two treatment groups and therefore multiplicity is not a concern. However, for comparisons of possible confounding variables across treatment groups, multiple testing may give rise to elevated type I error. For these analyses we will consider correcting the p-values via the Benjamini-Hochberg or other methods.

Statistically significant differences on overall comparisons will be explored using multiple pairwise comparisons of each of the (n) groups using Bonferroni correction for multiple comparisons. Mean scores and standard deviation for each group will be calculated. Subsequent multiple comparisons via Tukey's procedure will be set at 0.01 to control Type I error rate.

A Note on the Incidence of COVID 19 at 2 Years

The major reason for the large numbers of patients is to have a reasonable chance of demonstrating a difference in COVID-related complications in responders vs low/non-responders after receiving the Janssen Ad26.COv2.s vaccine. The risk of COVID 19 infections in patients without anti-SARS-CoV-2 spike protein antibody is unknown and the risk of COVID infection going forward in the US also is unknown. Over the past year prior to vaccination programs, the COVID infection rate in our patient population has been approximately 10% per year with death rates of approximately 2% overall per year.

The comparisons here are one-sample comparisons of Kaplan-Meier estimates of the incidence of infection or mortality versus historical incidences of 10% and 2%, respectively.

COVID Infection Rates: Using an assumed 10% infection rate per year as the null hypothesis in the 400 patients that had an undetectable or low mRNA vaccine response, an infection rate of less than 7% will result in 90% power to demonstrate statistical significance by the one-sample log-rank test.

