COVID-Related Mortality: For mortality, a reduction from an annual rate of death due to COVID of 2% in the non-responders to 0.7% in the responders would result in 80% power to demonstrate statistical significance by the one-sample log-rank test.

Interim Analysis

No formal interim hypothesis testing will be considered and therefore alpha-spending or control of type 1 error is not of concern for this study. Data summaries will be used throughout the study to audit data quality, to create reports for the regulatory requirements (i.e.. IRB, DMSB, etc.) and to ensure the overall study is running smoothly.

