6.9 Subject Population(s) for Analysis

The subject population for the primary analysis focus on the all-completed population, i.e. the patients who had undetectable antibody levels at the time of screening and were subsequently randomized in to either maintaining immunosuppression or altering it and completed the protocol requirements for the primary endpoint (n=300 total potential patients).

Secondary analyses will be broader and focus on the all-treated population (n=400 total patients). Patients with missing data may be excluded or their data can be imputed as mentioned above. Patients who did not have complete follow-up will be censored in any survival analyses at the time of their last follow-up.

The specific study populations are:

1. All enrolled patients (up to 1200)
 - a. Up to 800 with anti-SARS-CoV-2 spike protein antibody levels ≥ 250 U/ml who will not be administered the Janssen Ad26.COVID2.S vaccine but will be followed for 2 years for outcomes including COVID-19 infection.
 - b. 400 with anti-SARS-CoV-2spike protein antibody levels < 250 U/ml who will be administered the Janssen Ad26.CoV2.S vaccine.
2. All randomized population:
 - a. n=300 to receive the Janssen Ad26.COVID2.s vaccine with 150 to receive reduced immunosuppression and 150 to maintain current immunosuppression.
3. All-treated population:
 - a. n=400.
 - b. 100 patients with low anti-SARS-CoV-2spike protein levels (>0 to <250).
 - c. 300 patients with no anti-SARS-CoV-2 spike protein levels (0).
4. All patients receiving two doses of the Janssen Ad26.CoV2.S vaccine
 - a. Up to 250 patients from the treated population who meet entry criteria for Segment II
5. Protocol compliant population:
 - a. We do not anticipate a large percentage of patients will be non-compliant with the protocol. However, the protocol is sufficiently powered to account for compliance failures.
6. All-completed populations:

- a. For the treated patient populations the most important study related procedures (received Janssen Ad26.CoV2.S vaccine and follow-up testing) will be completed within 28 days.
- b. Patients will be monitored up to 2 years post-enrollment which overlaps with the routine clinical monitoring of transplant patients at our institutions.

7 Safety and Adverse Events

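### The powered COVID infection test compares all 400 treated patients with a pre-vaccination rate, so it cannot show the responder difference that justifies the sample size; the mortality power cannot be tied to one group

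*Combined protocol and SAP*

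**What the plan says.** All of this is in Section 6.8, under the note on COVID-19 incidence at 2 years, unless another section is named.

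- Purpose. The major reason for the large numbers is a reasonable chance of "demonstrating a difference in COVID-related complications in responders vs low/non-responders after receiving the Janssen" vaccine.
- Design. "The comparisons here are one-sample comparisons of Kaplan-Meier estimates of the incidence of infection or mortality versus historical incidences of 10% and 2%, respectively".
- Infection test. "Using an assumed 10% infection rate per year as the null hypothesis in the 400 patients that had an undetectable or low mRNA vaccine response", with 90% power claimed for a rate below 7% by the one-sample log-rank test.
- Source of the reference rates. "Over the past year prior to vaccination programs, the COVID infection rate in our patient population has been approximately 10% per year". The same paragraph says that "the risk of COVID infection going forward in the US also is unknown", and it puts mortality over that earlier period at "death rates of approximately 2% overall per year".
- Mortality test. 80% power, again by the one-sample log-rank test, for "a reduction from an annual rate of death due to COVID of 2% in the non-responders to 0.7% in the responders". No n is given.
- Population. Section 6.9: "Secondary analyses will be broader and focus on the all-treated population (n=400 total patients").
- Other survival methods. The main text of Section 6.8 names Kaplan-Meier estimation and Cox regression for time to infection or COVID death, and an interest in factors related to infection. It gives no groups, time origin or power.
- Sidedness. Section 6.7 makes two-sided 0.05 the default.

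**The concern.** The stated purpose is a contrast by response to the Janssen dose. The infection test groups patients by their earlier mRNA response and pools them. Response to the Janssen dose does not enter it, so no result of that test can show the stated difference. This matters for the design because Section 6.7 calls the randomised antibody comparison over-powered (30 per arm would suffice at the expected rates), which leaves the clinical contrast as the main argument for the size.

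The reference rate is also fragile. It describes the year before vaccination programs, and the plan itself calls future risk unknown. Section 5.6 restricts pre-exposure prophylaxis only until Day 28 (Segment I) or Day 84 (Segment II), and outside COVID-19 vaccine doses are recorded. A significant result could therefore reflect the epidemic or later protection rather than the study dose.

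The mortality statement puts the 2% in two places, overall in one paragraph and in non-responders in the next. It sets responders against non-responders but uses a test that has only one group.

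**Working it through.** **1. The plan's 90% for infection.** Inputs from Section 6.8: n=400, 10% vs 7% per year; two-sided 0.05 from Section 6.7; 2 years from Section 3.3; no dropout assumed. Reading the rates as annual probabilities, hazard = −ln(1−rate): 0.1054 and 0.0726, log ratio 0.373. Events expected under the null: 400 × (1 − 0.90²) = 76. Power = Φ(0.373 × √76 − 1.96) = Φ(1.29) = 90%. The figure is reproduced. Simulating the test itself, Z = (O − E)/√E with E the null hazard times follow-up, gives about 83% at exactly 7% two-sided and 90% at 6.7% two-sided or at 7.0% one-sided. As the plan says less than 7%, its 90% is not disputed.

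**2. What that test declares when the vaccine does nothing.** Same test, n=400, 2 years, two-sided 0.05, 40,000 simulated trials. The background rates are assumptions; the documents give none for the study period.

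| True background rate per year | Declares | Rate as probability | Rate as hazard |
|---|---|---|---|
| 8% | reduction | 0.455 | 0.406 |
| 7% | reduction | 0.826 | 0.775 |
| 12% | increase | 0.450 | 0.396 |

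**3. How many responders.** From Sections 6.7 and 3.1.2: 20% of 150 = 30; 60% of 150 = 90; low responders 60 (60% of 100) or 90 (the plan expects more than 90). After Segment I: 30 + 90 + 60 = 180, or 30 + 90 + 90 = 210. Segment II: (75 + 25) × 60% = 60, giving 180 + 60 = 240. If 90 low responders have already responded, only 10 remain: (75 + 10) × 60% = 51, giving 210 + 51 = 261. The range is 180–261.

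**4. Mortality, 0.7% vs 2% per year, 2 years, two-sided.** Simulated power of the one-sample test:

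| n | 180 | 210 | 240 | 261 | 400 |
|---|---|---|---|---|---|
| Power | 0.285 | 0.438 | 0.567 | 0.698 | 0.888 |

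At n=400, closed-form versions give 74% (null variance) and 87% (variance under the alternative); across formulas, 80% power needs 354–505 patients. One-sided, the 180–261 range becomes 54–84%. So 80% is compatible with all 400 treated patients, and near the top of a one-sided responders-only reading as well.

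**5. Power of the contrast the plan says it wants.** Schoenfeld: power = Φ(|ln HR| × √(D·p(1−p)) − 1.96), where D is expected events over 2 years and p the responder share; fixed groups, no dropout, no covariate adjustment. Example, 180 vs 220 at 7% vs 10%: D = 180 × 0.1351 + 220 × 0.19 = 66.1; p(1−p) = 0.2475; power = Φ(0.373 × 4.05 − 1.96) = 33%.

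The plan's 7% is a pooled rate. If it holds with low/non-responders at 10%, the responder rate is (400 × 7% − n₂ × 10%)/n₁, where n₁ is the number of responders and n₂ = 400 − n₁: (28 − 22)/180 = 3.3%; (28 − 19)/210 = 4.3%; (28 − 16)/240 = 5.0%; (28 − 13.9)/261 = 5.4%.

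| Responders / others | 7% vs 10% | 5% vs 10% | Pooled 7%, others 10% |
|---|---|---|---|
| 180 / 220 | 33% | 79% | 98% |
| 210 / 190 | 32% | 77% | 90% |
| 240 / 160 | 30% | 74% | 74% |
| 261 / 139 | 29% | 69% | 61% |

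Reading the rates as hazards lowers the minima to 26%, 65% and 56%.

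**The case against.** **A historical reference is understandable.** Section 6.7 rejects an unvaccinated control as unethical, and the plan discloses that future risk is unknown. That stands as a reason to report the comparison, but not as a reason to read its p-value as evidence about the study dose.

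**The pieces of a responder analysis are present.** Section 6.8 states the aim and names Cox regression. That also stands, and it makes the repair small. But no contrast, time origin or handling of Segment II is given. The initial mRNA responders offered as a comparison in Section 3.1.3 form a different contrast, and the secondary objective in Section 2 only estimates incidence.

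**A reader might infer that the responder contrast has only about 26–33% power.** The documents do not support that as a single figure. It places the plan's pooled 7% on responders alone; the pooled rate would then be 8.0–8.7%, so the plan's own alternative of below 7% would not be met. Keeping the pooled 7%, with low/non-responders at 10%, gives 56–98%.

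**A reader might infer that the mortality test has no population at all.** That is too strong. The sentence names responders and non-responders, and Section 6.9 defaults secondary analyses to the 400 treated patients, where the stated 80% is plausible. The fault is narrower: no n, two groups named for a one-group test, and two meanings for the 2%.

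**Scope.** Infection is labelled a primary clinical endpoint only in the footnote to the study schematic; Section 3.4 makes Day 28 antibody the primary endpoint.

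**Conclusion.** The concern holds for the secondary clinical objective and should be fixed. As written, the infection test cannot show the difference that the plan gives as its reason for the sample size, and its result moves with background risk: with no vaccine effect, about 40–45% false reductions at 8% per year, 78–83% at 7%, and about 40–45% false increases at 12%. These rest on assumed background rates, constant hazards and full 2-year follow-up. The mortality power is about 89% by simulation under the Section 6.9 default and about 28–70% if only responders are tested, two-sided, so the stated 80% does not identify the group.

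Two further inferences are not supported. The 90% infection power is not wrong, and the randomised comparison of antibody response is not touched.

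**What to change.** 1. State that, in the all-treated population, time to COVID-19 infection will be compared between responders (≥250 U/mL) and low/non-responders by Cox regression starting at the Day 28 test. Response is updated, not backdated, at the Segment II Day 84 test; calendar time is accounted for; and a short covariate list is fixed in advance from data already collected, for example baseline antibody group, number of mRNA doses, age and immunosuppression adjustment. Call the result an association, because response is not randomised.
2. Relabel the comparisons with 10% and 2% as descriptive.
3. Reconcile the two meanings of the 2%. State the mortality population and n and, for any power figure that stays, the sidedness and the power that matches them.
4. Give the power of the concurrent contrast over a range of assumed rates, with the assumptions listed: about 26–33% for 7% vs 10%, 65–79% for 5% vs 10%, and 56–98% if the pooled 7% holds with low/non-responders at 10%.
5. As an optional sensitivity analysis, censor at the first outside COVID-19 vaccine dose, whose date Section 5.6 requires. Censor at prophylaxis only if its dates are captured: Section 6.1.6 updates medications at Days 90 and 180, but Section 6.1.7 names only immunosuppression at Years 1 and 2. Note that such censoring may be informative if poor responders seek protection more often.

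The cost is SAP wording, a modest amount of extra analysis, a result that is observational, and a stated power that is less favourable than 90% over most of the range.

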Title	A Phase III, Randomized, Open Label, Clinical Trial Evaluating the Augmentation of Anti-SARS-CoV-2 Immunity in Kidney Transplant Recipients via a Heterologous Additional Dose with Janssen Ad26.CoV2.S Vaccine
Running Title	Additional Dose with Janssen Ad26.CoV2.S Vaccine in Kidney Transplant Recipients
Protocol Number	21-008036
Phase	III
Methodology	Prospective, randomized, open label clinical trial
Overall Study Duration	Three years.
Subject Participation Duration	Each subject will be followed for two years. Vaccinated subjects will be followed for two years after their last dose of the Janssen Ad26.CoV2.S vaccine.
Single or Multi-Site	Multiple (3 Mayo Clinic Transplant sites)
Objectives	
Primary Objectives
 
 1. To assess whether an anti-SARS-CoV-2 spike protein antibody level of ≥ 250 U/mL can be achieved 28 days after a dose of the Janssen Ad26.CoV2.S vaccine in kidney transplant recipients who did not form acceptable levels of anti-SARS-CoV-2 spike protein antibody (< 250 U/ml but > 0 U/mL) after receiving two or more doses of a mRNA vaccine: Pfizer-BioNTech (BNT162b2 vaccine) or Moderna (mRNA-1273). This includes any combination of the Pfizer-BioNTech (BNT162b2 vaccine) or the Moderna (mRNA-1273) results in two or more doses of mRNA vaccine. 2. To compare whether a dose of the Janssen Ad26.CoV2.S vaccine can achieve an anti-SARS-CoV-2 spike protein level ≥ 250 U/mL in kidney transplant recipients with no detectable anti-SARS-CoV-2 spike protein antibody after two or more mRNA vaccines. Kidney transplant recipients will be randomized to either maintenance of current immunosuppression or adjustment in immunosuppression around the time of receiving the Janssen Ad26.CoV2.S vaccine. The number of subjects with anti-SARS-CoV-2 spike protein level ≥ 250 U/mL between the two randomized groups will be compared.

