We have performed power calculations using several different assumptions regarding the expected outcomes table below. For example, if we expect that the true response rate of 20% of patients without anti-S antibodies at baseline without an adjustment to their immunosuppression will achieve the primary endpoint after receiving the Janssen Ad26.COVID-19 vaccine, then a true response rate of 37% in the patients in the altered immunosuppression group will reject the null hypothesis of an equal response rate with 90% power. Thus, 120 patients will still have low levels (< 250 U/ml) and 30 will have high levels (≥ 250 U/ml). Of the 100 with low levels prior to receiving the Janssen Ad26.COVID-19 vaccine, we expect that >90 will develop high levels.

Response rate in arm with no alteration in immunosuppression	Response rate in arm with alteration in immunosuppression	Power	Significance level (alpha)
20%	60%	1.00	0.05

10%	24%	0.9	0.05
20%	37%	0.9	0.05
30%	48%	0.9	0.05
23%	40%	0.9	0.05
32%	50%	0.9	0.05
41%	60%	0.9	0.05
52%	70%	0.9	0.05
63%	80%	0.9	0.05

Because we expect a true response rate of 20% and 60% in the patients without and with immunosuppression alteration, respectively, we acknowledge that this study is over-powered for the current enrollment targets. If these were the true response rates, 30 patients would be required for each arm to achieve 90% power. Therefore, even if there is drop out and/or misestimation of the response rates within each category then this study will be sufficiently powered for this comparison.

All tests will be carried out using two-side hypothesis tests with a significance level of 0.05 unless otherwise noted.

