8.5 Data Processing

A data coordinating group will monitor data collection and provide interim analyses to the Data Safety Monitoring Board. **We expect to complete Segment I enrollment within 6-9 months and have final data on the primary endpoint approximately 12 months from study start.** All patient outcome variables are tracked using registries set up in the “Healthy Planet” tool in the Electronic Health Record. For infection data, a registry flags patients as having an infection if a clinical diagnosis of COVID-19 was added to the problem list or a SARS-CoV-2 polymerase chain reaction test is positive. Those without laboratory confirmation are reviewed to ensure that this was appropriate (for example, an outside laboratory result not visible in our chart). External results could satisfy registry metrics if they could be identified within the interoperable framework for data sharing across the EHR, Care Everywhere (Epic Systems Corporation). A similar registry architecture captures data on vaccination data, populated from both EHR records, state health registries, and the health information exchange.

Data Security and Confidentiality

Source documents, CRFs and original consents will be stored in secured locations at Mayo Clinic. Clinical laboratory values are stored in the electronic medical record system requiring protected password access and approved use. Every individual who accesses a medical record has their activity tracked in the system. These data are monitored regularly for access and a formal policy regarding protection of personal privacy which is in place throughout Mayo Clinic.

Data Quality Assurance

Manual and computerized quality checks will occur during data collection and analyses and any discrepancies will require Case Report Form (CRF) review and validation of correct data.

Data Clarification Process

All queries will be logged and tracked electronically, as well as any corrections or justifications which are made, if applicable.

Records Retention

The sponsor-investigator will maintain records and essential documents related to the conduct of the study. These will include subject case histories and regulatory documents.

The sponsor-investigator will retain the specified records and reports for

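### Under the plan's own two-sided 5% rule and two-year follow-up, power for the COVID-19 infection comparison at 7% per year is about 82%, not the stated 90%

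*Combined protocol and SAP*

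**What the plan says.** Section 6.8, in the note on COVID-19 incidence, describes the design: "The comparisons here are one-sample comparisons of Kaplan-Meier estimates of the incidence of infection or mortality versus historical incidences of 10% and 2%, respectively". For infection it sets the hypothesis "Using an assumed 10% infection rate per year as the null hypothesis in the 400 patients" with an undetectable or low mRNA vaccine response, and then claims that "an infection rate of less than 7% will result in 90% power to demonstrate statistical significance by the one-sample log-rank test". For COVID-related death it starts from 2% per year in the non-responders and says that a reduction "to 0.7% in the responders would result in 80% power to demonstrate statistical significance by the one-sample log-rank test".

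Neither sentence gives an alpha level, sidedness, length of follow-up or loss rate. The mortality sentence also gives no sample size. The missing items have to come from elsewhere:

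- Section 6.7: "All tests will be carried out using two-side hypothesis tests with a significance level of 0.05 unless otherwise noted". The incidence note states no exception.
- Study Summary: "Each subject will be followed for two years". Section 3.3 agrees, and the note itself is titled "A Note on the Incidence of COVID 19 at 2 Years".
- Section 6.9 censors patients with incomplete follow-up at their last contact.

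**The concern.** With the plan's general rules put into the infection sentence, the 90% does not come out at 7%. If 82% is right, the chance of missing a true 7% rate is about 18%, against the 10% that the sentence implies. A reader who takes the sentence at face value would also read a non-significant result as stronger evidence against a reduction than it is. The mortality sentence cannot be checked at all until its population and n are fixed.

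**Working it through.** **Inputs.** Null rate 10% per year, alternative 7% per year, N = 400, one-sample log-rank (section 6.8); two-sided 0.05 (section 6.7); two years per subject (Study Summary, section 3.3). Assumptions: exponential event times, rates read as annual risks, no loss to follow-up.

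**Formula.** The statistic is Z = (O − E)/√E, with O the observed events and E the events expected under the null hazard.

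- Hazards: h0 = −ln(0.90) = 0.10536; h1 = −ln(0.93) = 0.07257; c = h0/h1 = 1.4518.
- Two-year event probability under the alternative: p = 1 − 0.93² = 0.1351.
- Mean of O = 400 × 0.1351 = 54.0. Mean of E = 1.4518 × 54.04 = 78.5.
- With q = 1 − exp(−2·h1)·(1 + 2·h1) = 0.00957, the per-patient variance of O − E is p + 2c²q − 2cq − (cp − p)² = 0.1439, square root 0.3794.
- Power = Φ{[√N·(cp − p) − z·√(cp)] / 0.3794}, where √400 × 0.06104 = 1.2209 and √(cp) = 0.4429.

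**Reproducing the plan's figure.** One-sided 5%, z = 1.645: (1.2209 − 0.7285)/0.3794 = 1.298, power 90.3% (simulation 90.0-90.4%). This matches the stated 90%.

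**Under the plan's rule.** Two-sided 5%, z = 1.960: (1.2209 − 0.8680)/0.3794 = 0.930, power 82.4% (simulation 82.4-83.0%). Reaching 90% two-sided at 7% would take N = 493.

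**Sensitivity, two-sided 5%.**

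| Variant | Power |
|---|---|
| True rate 6.9% / 6.8% / 6.7% | 85.2% / 87.7% / 89.9% |
| Rates read as hazards 0.10 and 0.07 | 77% |
| Variance taken as (O + E)/2, rate 7% | 85-86% |
| Assumed loss of 5% per year | about 81% |
| Assumed loss of 10% per year | 78-79% |
| 56 extra days for 100-250 Segment II patients | 83-84% |
| Accrual over 0.5 / 0.75 / 1 year, at least 2 years each, common end | 86.5% / 88.2% / 89.7% |

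**Mortality, 2% against 0.7%, two years.** At n = 400 only about 400 × (1 − 0.993²) = 5.6 deaths are expected, so simulation is safer than the formula. It gives about 89% two-sided and 94% one-sided (formula 86.3% and 94.7%). Neither is 80%.

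If the test is in responders only, the rates in section 6.7 imply 30 (20% of 150) + 90 (60% of 150) + 60 to 90 low responders = 180 to 210, or 240 to 270 with the 60 responders expected in Segment II. With the standard statistic, two-sided power is below 80% throughout: 44% at 210, 57% at 240 and 67% at 270. No range is worth quoting, because so few deaths make power jump with n (28% at 180, 51% at 190). It also depends on the statistic: the averaged variance gives 54% at 180 and, in the same simulation, slightly more than 80% at 270.

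**The case against.** The best defence is that the sentence is under-specified rather than wrong. The alternative is written as below 7%, and 6.7% both satisfies that and rounds to 7%; there, two-sided power is about 90%. With the averaged variance even 6.8% comes to about 90%. A three-year study with one year of accrual and a common end also gives close to 90% two-sided.

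Part of this stands. These routes show that the 90% need not have come from a one-sided test. They do not rescue the sentence as written. Rates just under 7% are covered by it and fall short. The accrual route needs follow-up beyond the two years per subject that the plan sets, and section 8.5 says "We expect to complete Segment I enrollment within 6-9 months", which gives at most about 88% even with a common end.

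On mortality, section 6.8 introduces both tests together and names only the 400, and section 6.9 puts secondary analyses on the all-treated 400. On that reading the stated 80% is conservative. The wording about responders points the other way, and the documents do not settle it.

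It also stands that infection incidence is a secondary endpoint, that the plan calls future infection risk unknown, and that 82% is still a conventional level of power.

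**Conclusion.** The point holds as a discrepancy in the stated power. At exactly 7% per year, 400 patients, fixed two-year follow-up and two-sided 0.05, power is about 82% with the standard statistic and no loss. It is roughly 77-86% across statistics and readings of the rate, and about 81% with an assumed 5% per year loss. No two-sided version at 7% with fixed two-year follow-up gives 90%.

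Three stronger readings are tempting and not supported:

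- A reader might infer that the 90% was computed one-sided. The match is close (one-sided 90% needs N = 396), but the documents never say so, other routes reach about 90%, and the mortality figure does not fit a one-sided convention at n = 400 (94% against the stated 80%).
- A reader might infer that the mortality comparison is badly underpowered. That depends on a responder count built from the plan's assumed rates and on a population that the plan does not fix.
- A reader might infer that the justification for the trial's size fails. The sentence in section 6.8 giving the main reason for the large numbers concerns responders against low or non-responders, not the pooled 400 against a historical rate.

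The primary randomised antibody comparison is unaffected.

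**What to change.** In section 6.8, restate the infection sentence along these lines: about 82% power at a true rate of 7% per year (about 90% at 6.7%) against 10%, one-sample log-rank, two-sided 0.05, 400 patients with two-year follow-up. Add that the rates are annual risks and name the variance used in the statistic. If a one-sided test was intended, it has to be written as an exception to section 6.7.

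For mortality, name the analysis set and its n and give the matching two-sided power: about 89% if all 400; below 80% with the standard statistic if only the roughly 180-270 responders implied by section 6.7.

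The cost is wording only. Sample size, test and population stay as they are. The infection figure becomes less favourable; the mortality figure moves up or down with the set chosen.
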